6.1. Primary outcome (Hypothesis 2)

Hypothesis 2: Overall >50% of symptom burden is nocebo rather than pharmacological.

For the trial, all participants receive a smartphone or, if they prefer, the application can be downloaded to their existing phone. Access to the phone will allow them to record real-time daily documentation of symptoms experienced on a visual analogue scale of 0-100.

Participants will rate symptoms every day, with the daily scores averaged into a monthly score.

SAMSON STATISTICAL ANALYSIS PLAN

January 14, 2020

Page 6

Each participant receives four months (4×28 days) each of no medication, placebo, and active medication (i.e, statin). We represent the individual participant's symptom score data as follows:

$$\begin{array}{ccc} x_{0_1} & x_{p_1} & x_{s_1} \\ x_{0_2} & x_{p_2} & x_{s_2} \\ x_{0_3} & x_{p_3} & x_{s_3} \\ x_{0_4} & x_{p_4} & x_{s_4} \end{array}$$

$$\bar{x}_0 = \frac{\sum_{j=1}^4 x_{0_j}}{4} = \frac{\sum_{j=1}^4 ((\sum_{i=1}^{28} x_{0_{ij}})/28)}{4}, \bar{x}_p = \frac{\sum_{j=1}^4 x_{p_j}}{4} = \frac{\sum_{j=1}^4 ((\sum_{i=1}^{28} x_{p_{ij}})/28)}{4}, \bar{x}_s = \frac{\sum_{j=1}^4 x_{s_j}}{4} = \frac{\sum_{j=1}^4 ((\sum_{i=1}^{28} x_{s_{ij}})/28)}{4}$$

\bar{x} - mean symptom score for no medication, placebo, statin, i -day 1 to 28 of treatment month, j - treatment month 1 to 4

We assume no carry-over effect. Thus, the estimated mean of the effect of nocebo is calculated as follows:

$$\text{Mean nocebo effect} = \sum_{n=1}^N \left(\frac{\bar{x}_{p_n} - \bar{x}_{0_n}}{\bar{x}_{s_n} - \bar{x}_{0_n}} \right) / N$$

N = number of study participants

Because the study participants are independent of each other, the variance of the estimated mean can be calculated as the sum of variances of the individual participants:

$$\text{Variance of the mean nocebo effect} = s^2 = \sum_{n=1}^N s_n^2 = \sum_{n=1}^N \text{Var} \left(\frac{\bar{x}_{p_n} - \bar{x}_{0_n}}{\bar{x}_{s_n} - \bar{x}_{0_n}} \right)$$

To calculate the variance of the estimate, we use a Taylor series approximation, which is a function of the variance of the numerator, variance of the denominator, and the covariance of the two:

$$1) \text{Var}(\text{numerator}) = \text{Var}(\bar{x}_p - \bar{x}_0) = s_p^2 + s_0^2 - 2r_{s_p, s_0} s_p s_0$$

$$2) \text{Var}(\text{denominator}) = \text{Var}(\bar{x}_s - \bar{x}_0) = s_s^2 + s_0^2 - 2r_{s_s, s_0} s_s s_0$$

CONFIDENTIAL

$$3) \text{ Cov}(numerator, denominator) = \text{cov}(\bar{x}_p - \bar{x}_0, \bar{x}_s - \bar{x}_0) = \text{cov}(\bar{x}_p, \bar{x}_s) - \text{cov}(\bar{x}_p, \bar{x}_0) - \text{cov}(\bar{x}_0, \bar{x}_s) + \text{cov}(\bar{x}_0, \bar{x}_0) = \text{cov}(\bar{x}_p, \bar{x}_s) - \text{cov}(\bar{x}_p, \bar{x}_0) - \text{cov}(\bar{x}_0, \bar{x}_s) + s_0^2$$

$$\text{where, for example, } \text{cov}(\bar{x}_p, \bar{x}_s) = \frac{\sum_{j=1}^4 (x_{p_j} - \bar{x}_p)(x_{s_j} - \bar{x}_s)}{4 - 1}$$

$$4) s_n^2 = \text{Var}\left(\frac{\bar{x}_p - \bar{x}_0}{\bar{x}_s - \bar{x}_0}\right) = \left(\frac{\bar{x}_p - \bar{x}_0}{\bar{x}_s - \bar{x}_0}\right)^2 \left(\frac{\text{Var}(\bar{x}_p - \bar{x}_0)}{(\bar{x}_p - \bar{x}_0)^2} + \frac{\text{Var}(\bar{x}_s - \bar{x}_0)}{(\bar{x}_s - \bar{x}_0)^2} - 2 \frac{\text{cov}(\bar{x}_p - \bar{x}_0, \bar{x}_s - \bar{x}_0)}{(\bar{x}_p - \bar{x}_0)(\bar{x}_s - \bar{x}_0)}\right)$$

s = standard deviation, s² = variance, r = correlation

The Taylor's series approximation is based on asymptotic theory. Should the data not allow stable estimates of the components of the variance, we will use a bootstrapped estimate of the variance.

To calculate the 95% CI for the mean nocebo effect, the test statistic is $t = \sqrt{N}(\mu - \mu_0)/\sqrt{s^2}$

The null hypothesis is rejected if $t > t_{\alpha, N-1}$ where, in SAS, $t_{\alpha, N-1}$ is TINV(1- α , N-1);

In SAS, the p value associated with the test statistic T is PVAL=1-probt(abs(T), N-1) or PVAL=cdf('T', T, N-1).

The 95% confidence interval is $\text{Mean nocebo effect} \pm t_{\alpha/2, N-1} \sqrt{s^2} / \sqrt{N}$

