8 STATISTICAL AND DATA ANALYSIS

Our study's principal hypotheses will be tested as follows:

Hypothesis 1 will be tested by calculating the proportion of respondents completing the study, and the corresponding 95% confidence interval for this estimate, and examining whether the confidence interval lies completely above a value of 0.3 or not.

To test **Hypothesis 2**, comparisons between the average monthly symptom burden (measured by the monthly aggregate of symptom scores) resulting from no treatment/placebo/statin treatment periods will be made using a longitudinal multilevel model. The most basic model to test hypothesis 2 would be:

To test **Hypothesis 2**, we will calculate the nocebo ratio across all patients. This is to avoids attempting to analyse the pathological distributions that would arise for patient whose mean statin symptom score is close or less than their no treatment score, because the nocebo ratio becomes disruptively extreme. Combining the data

Confidential Page 14 of 22

SAMSON Protocol No: 1.4

Version 1.4 10th April 2020

across all patients to yield a single statin, placebo and no treatment symptom score allows a representative and interpretable nocebo ratio to be provided.

Hypothesis 3 is that the majority of patients will be taking statins, or have a non-side effect reasons for not doing so, at 6 months after study completion. This will be a descriptive statistic of the sample, which does not require inference of the population mean. No further statistical analysis is therefore necessary

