This statistical analysis plan (SAP), which is based on protocol Version 1.2 dated August 1, 2019, defines the methods and analyses that Imperial College London plans to use to analyze the data from the Self-Assessment Method for Statin side effects Or Nocebo trial (henceforth, SAMSON). This study adheres to the principles outlined in the Medicines for Human Use (Clinical Trials) Regulations 2004 (SI 2004/1031), amended regulations (SI 2006/1928), and the International Conference on Harmonisation Good Clinical Practice (ICH GCP) guidelines. It is being conducted in compliance with the protocol, the Data Protection Act, and other regulatory requirements as appropriate. If the protocol is subsequently amended, this SAP may be amended as well. Should the SAP and the protocol be inconsistent with respect to the planned analyses, the language of the SAP is governing.

2. Investigational plan

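### SAP 6.1 still makes the average of individual nocebo ratios the primary estimate, with no rule for near-zero or negative denominators, although protocol v1.4 replaced it with one pooled ratio

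*SAP*

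**What the plan says.** SAP 6.1 labels Hypothesis 2 the primary outcome: "Hypothesis 2: Overall >50% of symptom burden is nocebo rather than pharmacological". It averages daily scores to months and months to one mean per condition for each participant. It then gives the estimator ("Thus, the estimated mean of the effect of nocebo is calculated as follows"): the sum over participants of (placebo − none)/(statin − none), divided by N. A Taylor-series variance, a t test and a 95% interval follow. A bootstrap is the fallback if the variance components are unstable. SAP 6.1.1 sets the conditions for computing a ratio, and all of them concern missing scores.

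Protocol v1.4 section 8 (10 April 2020) says "we will calculate the nocebo ratio across all patients", combining data "across all patients to yield a single statin, placebo and no treatment symptom score". Its reason is the distribution that arises for a patient "whose mean statin symptom score is close or less than their no treatment score, because the nocebo ratio becomes disruptively extreme".

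The SAP is dated 14 January 2020 and describes itself as a plan "which is based on protocol Version 1.2 dated August 1, 2019". On precedence its introduction says: "Should the SAP and the protocol be inconsistent with respect to the planned analyses, the language of the SAP is governing". On updating it says only: "If the protocol is subsequently amended, this SAP may be amended as well".

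**The concern.** The two current documents name different primary estimators, and the precedence clause selects the one that the later document abandons as unstable. A participant whose statin and no-treatment means nearly coincide contributes a ratio of arbitrary size and sign, and nothing in the SAP limits it. The bootstrap fallback changes the variance and leaves the point estimate alone; 6.1.1 excludes only for missing data. The headline claim that more than half of the symptom burden is nocebo could therefore turn on one person. With two estimators on file, the choice between them could also be made after the results are known.

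**Working it through.** **The plan's own figure.** SAP 4.1 sizes Hypothesis 2 for a half-width of 0.10, assuming individual ratios uniform on 0 to 1 (SD 0.29). The printed formula gives (1.96 × 0.29/0.10)² = 32.3, so 33, where the SAP prints 36. The slip is harmless: at the planned N = 50 the half-width is 1.96 × 0.29/√50 = 0.080. But that precision needs ratios confined to 0–1, which the estimator does not ensure.

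**One participant.** SAP 4.1 reports 60 randomised. Assume 59 with numerator 8 and denominator 10 (ratio 0.80) and one with numerator 5.
- Denominator 0.1: average of ratios (59 × 0.80 + 50)/60 = 1.62; pooled 477/590.1 = 0.81.
- Denominator −0.1: average (47.2 − 50)/60 = −0.05; pooled 477/589.9 = 0.81.
- The average is at or below 0.5 when 5/d ≤ 30 − 47.2 = −17.2, that is, for any d from −0.29 up to 0.

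**Simulation.** The documents give no score means or SDs, so these are assumptions: N = 60, four months per condition, month-to-month SD 1, the same true share of 0.70 for everyone. The statin excess (statin − none) varies between people as shown. There were 20,000 trials per setting; at 1–2 SD the range limits for the average of ratios move by a few tenths between runs.

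| Setting | Mean excess | Person SD | Average of ratios, central 95% | Pooled ratio, central 95% | Average ≤ 0.5 | At least one denominator ≤ 0 |
|---|---|---|---|---|---|---|
| a | 1 | 0.5 | −4.1 to 5.6 | 0.54 to 0.87 | about 35% | >99.9% |
| b | 2 | 0.5 | 0.0 to 1.5 | 0.62 to 0.78 | 7% | 47% |
| c | 2 | 1.0 | −1.0 to 2.4 | 0.62 to 0.78 | 19% | 96% |
| d | 3 | 0.5 | 0.65 to 0.79 | 0.65 to 0.75 | 0.3% | about 1.5% |
| e | 4 | 0.5 | 0.66 to 0.75 | 0.66 to 0.74 | 0% | 0% |

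The pooled figure for setting a can be checked directly. The pooled ratio is ≤ 0.5 when the mean of (numerator − 0.5 × denominator) is ≤ 0. Per person this quantity has mean 0.2 and variance 0.2² × 0.5² + 0.25 × (1 + 0.25 + 0.25) = 0.385. So z = 0.2/√(0.385/60) = 2.50, a probability of about 0.6%. It is smaller in the other settings.

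Two variations:
- With shares uniform on 0.4–1.0, the average is ≤ 0.5 in 35%, 8%, 19%, 0.3% and 0% of trials, and the pooled ratio in 0.9% or fewer.
- Under SAP 4.1's own uniform 0–1 scatter (true share 0.50), the average misses by more than 0.10 in 84%, 42%, 63%, 8% and 3% of trials; the pooled ratio misses by that much in 27%, 7%, 8%, 3% and 2%.

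**The printed standard error.** A mean of N independent ratios has variance Σsₙ²/N². SAP 6.1 gives Σsₙ², then divides its root by √N only. The result, √(Σsₙ²)/√N, exceeds the correct √(Σsₙ²)/N by √N, or √60 = 7.7.

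Take a stable case: every participant has excess 4 and share 0.70. With four-month means, the numerator and denominator variances are each 2 × 1/4 = 0.5 and their covariance is 0.25. Then sₙ² = (0.5 + 0.49 × 0.5 − 2 × 0.70 × 0.25)/16 = 0.0247, and Σsₙ² = 1.48.
- Printed: SE = √1.48/√60 = 0.157, t = 0.20/0.157 = 1.3.
- Correct: SE = √1.48/60 = 0.020, t = 0.20/0.020 = 10.

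The one-sided 5% critical value is about 1.67, so the printed test fails where the data are clear. The SAP's covariance formula also divides by 3 without the further division by 4 that a four-month mean needs; as printed, t halves again. In simulation the printed test rejected in 0% of trials in all five settings, and in 0–0.1% when sₙ² was read as the variance of a four-month mean.

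**The two estimators differ even without noise.** Take 30 people with excess 20 and share 0.4, and 30 with excess 5 and share 0.8. The average of ratios is 0.60; the pooled ratio is (30 × 8 + 30 × 4)/(30 × 20 + 30 × 5) = 360/750 = 0.48.

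**The case against.** The strongest reply is that the sponsor has already solved the problem. Protocol v1.4 names the denominator difficulty and adopts the pooled ratio, while the SAP predates it and foresees amendment. That stands as a description: this is a failure to update the SAP, and the trial design is not at fault. It does not remove the defect, because the precedence clause favours the SAP and amendment is optional.

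Second, the simulated harm rests on assumed inputs. Entry requires withdrawal for side effects that began within two weeks (protocol 4.1), which might favour larger denominators. That is fair, and at 3–4 SDs the risk to the point estimate is small.

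Third, a reader might infer that the SAP would falsely declare Hypothesis 2 supported. The documents do not support that. A tiny denominator inflates sₙ² as well as the ratio, and the printed variance makes rejection rarer still; the likely error is a test that almost never rejects.

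Fourth, a reader might infer that participants are given an unstable ratio with nothing beside it. Protocol 3.4 does show them their individual proportion, but Figure 1 in protocol 1.2 also has them look at the sorted months, so this part is partly handled.

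**Conclusion.** The point holds and should be corrected before analysis. Two parts need no assumption: SAP 6.1 and protocol v1.4 section 8 name different primary estimators, with the SAP prevailing as written, and the SAP has no rule for denominators at or near zero. The printed variance error is also a matter of algebra.

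The size of harm is conditional and concerns the point estimate. With a true share of 0.70 and N = 60, the average of ratios is at or below 0.5 in about 35%, 7%, 19%, 0.3% and 0% of trials in settings a–e, against about 0.6% or fewer for the pooled ratio. It is serious when the mean statin excess is one to two monthly SDs and small at three to four; the documents do not say where this trial lies. Nor do they show that the rejected estimator was ever applied, since a later SAP cannot be excluded.

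**What to change.** First confirm whether a later SAP exists. If not, amend SAP 6.1 as follows.

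1. Make the primary estimate the mean over participants of (placebo − none) divided by the mean over participants of (statin − none).
2. State that this is the overall share of symptom burden. It weights individual shares by the size of the statin excess, which fits the wording of Hypothesis 2, but it can differ from the average individual share and fall on the other side of 0.5.
3. Replace the variance formula with a participant bootstrap or Fieller interval for the pooled ratio. Under uniform 0–1 scatter in settings a, b, c and e, coverage was 94.7–95.2% for Fieller and 92.8–95.5% for the bootstrap.
4. State the test level. A lower bound above 0.5 from a two-sided 95% interval is a one-sided 2.5% test. SAP 6.1 uses an unspecified one-sided alpha and 6.2.1 uses 0.05; keeping one-sided 5% means using the lower bound of a 90% interval.
5. Reconcile this with protocol 8.1, which says that Hypothesis 2 addresses only the sample, and restate SAP 4.1 as precision of the pooled ratio. Also state the role of the multilevel-model paragraph in protocol 8.

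Keep individual ratios descriptive. A flag for denominators at or near zero, and the handling of an unbounded Fieller set, are options for the sponsor. Flagged participants should stay in the pooled ratio: dropping them and still averaging ratios gave a median of 0.64 against a true 0.70 in setting a.

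The cost is text in SAP 4.1 and 6.1 and protocol 8 and 8.1, with no new data or patients. The downside is the change of estimand in item 2.

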2.4. Randomization

Eligible participants are enrolled on InForm, which allocates each participant a random predefined order during which to take the study interventions. The Imperial Clinical Trials Unit (ICTU) generates these random codes and supplies them to the production pharmacy.

3. Study schedule

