3.2. Unscheduled visits

Unscheduled assessments are not performed unless participants develop adverse events that the chief investigator considers 'related' to the trial procedure or to atorvastatin therapy.

4. Sample size determination and power calculation**4.1. Sample size calculation – Hypothesis 2**

Each "effect of nocebo" will be a value which, for the sake of the calculation in the protocol, was assumed to be between 0 and 1. The study aims to report an average effect of nocebo for

the population that has a 95% CI of $\pm 10\%$. To achieve this, assuming a conservative scenario of individual-participant values scattered uniformly from 0 to 1 (i.e., $SD = 1/\sqrt{12} = 0.29$), the number of participants to be studied will need to be $\geq N$ where $0.29/\sqrt{N} \leq 0.10/1.96$ (i.e., $N > (1.96 \times 0.29/0.10)^2 = 36$). The investigators planned to recruit 50 participants. In all a total of 62 participants were screened and 60 were randomized.

5. Statistical analysis: general considerations and conventions

Descriptive and inferential statistics will be used to summarize results of the SAMSON study. Continuous variables will be summarized using the number of subjects (N), mean, SD, median, 25th and 75th percentiles, and minimum and maximum. Discrete variables will be summarized using counts and percentages.

Summaries will be provided for demographics, medical history, concomitant medications, and adverse events. For summaries of medical history, concomitant medications, and AEs, the Medical Dictionary for Regulatory Activities (MedDRA®) and the World Health Organization Drug dictionaries, as appropriate, will be used.

All data listings, summaries, and statistical analyses will be generated using SAS® Version 9.4 (or higher) or other validated software.

6. Efficacy analysis

As described in Section 2.3, the study has three hypotheses.

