6.1.1. Missing and partial data for primary outcome

For the calculation of mean symptom score for particular treatment (statin, placebo, no medication) missing scores ($i < 28$) will be handled by only using study months that have at least 10 of daily symptom scores non-missing. We will perform sensitivity analyses using different thresholds for non-missing scores (such as 14 and 16 non-missing scores) and compare the percentage of missing symptoms scores during the 'pill' months (statin or placebo) versus 'no pill' months. We will assess the temporal pattern of missing symptom scores by comparing the percentage of missing scores at the beginning of the study to the percentages at later study months.

The nocebo effect for an individual participant will be calculated only if he or she has non-missing symptom scores for at least one month of each treatment ($j \geq 1$). If the participant has not recorded any symptom score for one of the three treatments ($j=0$ for statin, placebo, or no pill) the nocebo effect cannot be calculated, and the primary endpoint analysis will exclude that participant.

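### SAP 6.1 treats the plain sum of N participant variances as the variance of their mean, so the primary interval and test are sqrt(N) too wide for the SAP's own model and do not tighten with sample size

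*SAP*

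**What the plan says.** SAP 6.1 computes for each participant the placebo-minus-none difference over the statin-minus-none difference, sums these ratios over participants and divides by N. For the error it states that "the variance of the estimated mean can be calculated as the sum of variances of the individual participants", and the displayed formula agrees: s² is the sum of the s_n², with no division.

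The next step begins "To calculate the 95% CI for the mean nocebo effect, the test statistic is" and gives t = sqrt(N)(μ − μ0)/sqrt(s²). The interval is the mean ± t × sqrt(s²)/sqrt(N). Both use the summed s².

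Each s_n² comes from a Taylor-series formula built on variances and covariances of the three conditions. The key reads "s = standard deviation", and the one divisor printed, for a covariance, is 4 − 1. There is a fallback: "Should the data not allow stable estimates of the components of the variance, we will use a bootstrapped estimate of the variance".

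SAP 4.1 plans differently. It wants an average for "the population that has a 95% CI of" ±10%, "assuming a conservative scenario of individual-participant values scattered uniformly from 0 to 1" (SD 0.29), with standard error 0.29/sqrt(N).

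Protocol 8 describes a pooled ratio over all patients, and Protocol 8.1 says Hypothesis 2 concerns the sample only. The SAP's introduction makes the SAP govern where the two differ.

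**The concern.** A mean of N independent quantities has variance equal to their summed variances over N². SAP 6.1 starts from the sum and divides by N once, so one factor of N is missing. What remains is the error of a typical single participant.

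This is the governing analysis of the primary outcome. If it is programmed as written, the reported interval has almost nothing to do with the number of people studied, and the ±10% that justified the sample size has no link to the analysis. The likely result is a failure to show Hypothesis 2 when the data support it.

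Two further problems sit in the same formulas. The variance components appear to be those of single months, where variances of four-month means are needed. And nothing in the formula reflects scatter between participants, the only quantity SAP 4.1 plans on.

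**Working it through.** **Inputs from the documents.** N = 50 planned and 60 randomised (SAP 4.1); SD 0.29 and target ±0.10 (SAP 4.1); null value 0.50 (Hypothesis 2). The documents give no s_n, monthly SD or effect size. The SAP states no alpha for this test; one-sided 0.05 is assumed below.

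**The plan's own precision figure.** The expression printed in SAP 4.1 gives (1.96 × 0.29/0.10)² = 32.3, so 33, where the SAP prints 36. A t quantile gives 35. This small mismatch is a separate matter. What counts here is that SAP 4.1 uses SD/sqrt(N), which shrinks with N.

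**Algebra.** Let RMS be the root mean square of the s_n, so that the sum of the s_n² is N × RMS².

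- SAP 6.1: SE = sqrt(N × RMS²)/sqrt(N) = RMS.
- Correct for the same model: SE = sqrt(N × RMS²)/N = RMS/sqrt(N).
- Ratio: sqrt(N), for equal or unequal s_n. That is 6.0, 7.07 and 7.75 at N = 36, 50 and 60.

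**What ±0.10 would require.** The largest permissible RMS is 0.10/t under SAP 6.1 and 0.10 × sqrt(N)/t when done correctly:

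| N | t(0.975, N−1) | SAP 6.1 | Correct |
|---|---|---|---|
| 36 | 2.030 | 0.049 | 0.296 |
| 50 | 2.010 | 0.050 | 0.352 |
| 60 | 2.001 | 0.050 | 0.387 |
| 240 | 1.970 | 0.051 | 0.786 |

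The SAP column is flat; only the t quantile moves.

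**Months.** The printed covariance of two four-month means uses divisor 4 − 1 with no further division by 4, and the derivation sets the covariance of the no-medication mean with itself equal to s_0². Read that way, every component is a single-month quantity and s_n is doubled when four months are usable. The combined factors would be 12.0, 14.1 and 15.5 at N = 36, 50 and 60. The SAP prints no divisor for the variances themselves, so this second factor depends on the reading.

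**Illustration with assumed inputs.** Independent normal monthly means with SD 1, four months per condition, SAP 6.1 coded as written with single-month components, and median half-widths. With a statin-minus-none difference of 10 monthly SDs and a common nocebo share of 0.70:

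| N | SAP half-width | Actual 95% range | SAP test rejects 0.5 | Corrected test |
|---|---|---|---|---|
| 36 | 0.258 | ±0.020 | 22% | 100% |
| 60 | 0.254 | ±0.016 | 22% | 100% |
| 240 | 0.250 | ±0.008 | 10% | 100% |

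In this setting more participants give less power. With the N error alone, without the months factor, the half-width at N = 60 is 0.127.

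**Between-participant scatter.** With shares uniform on 0 to 1 as in SAP 4.1, 10 SDs and N = 60, SAP 6.1 gives ±0.261. Correcting only the algebra gives ±0.017, too narrow for a population mean, whose actual range is ±0.076. The SD of the ratios over sqrt(N) gives ±0.077 with 95% coverage.

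**The case against.** The algebra is hard to contest: the words, the displayed sum, the test and the interval all agree, and the division by N survives in the estimator just above, so this is not text damage. The serious objections concern scope and remedy.

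- **The sqrt(N) factor belongs to the within-participant model.** Against a population mean it is smaller: 0.261/0.077 = 3.4 in the uniform-share example. With a between-participant SD of 0.29, the SAP interval would be too narrow if the typical s_n were below about 0.041 (N = 50) or 0.038 (N = 60). This stands as a limit on the size, not a defence of the formula.
- **The months factor is an inference.** This stands; it is kept conditional.
- **The bootstrap may reverse the direction.** If it returned the variance of the mean and the interval then divided by N again, the interval would be sqrt(N) too narrow. The SAP does not say what is resampled or where the result enters. This stands, and is a reason to delete the sentence.
- **The later protocol uses a pooled ratio and a sample-only target.** The SAP is based on protocol 1.2; the protocol in hand is 1.4. The SAP governs as written, but the two must be reconciled. For a sample-only target, the SD of the ratios over sqrt(N) would be the wrong error.
- **The replacement may also fail to tighten.** With differences varying between people (mean 5, SD 3 monthly SDs, share 0.70), its half-width was 0.135, 0.139, 0.128 and 0.128 at N = 36, 60, 240 and 960. At 3 SDs for everyone, bias in the ratio cut coverage to 86% at N = 240. This stands: near-zero denominators are a defect of the estimand, which no variance formula repairs.

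**Conclusion.** Wrong as written; must be fixed before the primary analysis is run. For the SAP's own model of independent participants and within-participant error, the standard error is too large by exactly sqrt(N), 7.1 at 50 and 7.7 at 60, and by twice that if the variance components are single-month and four months are usable. If fewer participants are analysable, the factor is the square root of that number.

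For the population mean that SAP 4.1 aims at, the factor is below sqrt(N) and depends on quantities the documents do not give. In every assumed setting run, the SAP interval was still wider than the one based on the SD of the ratios. The direction is conservative, apart from the undefined bootstrap fallback and the case of very small s_n.

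**What to change.** In SAP 6.1, replace the sum-of-variances line, items 1 to 4, the bootstrap sentence, the test and the interval with:

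> Let q_n be participant n's ratio and SD_q the sample SD of the N ratios. SE = SD_q/sqrt(N). The 95% CI is mean ± t(0.975, N−1) × SE. The test is t = (mean − 0.5)/SE, with one-sided p = 1 − probt(t, N−1).

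This is the standard error SAP 4.1 already plans on. It needs no within-person variances, which matters because SAP 6.1.1 computes a ratio "only if he or she has non-missing symptom scores for at least one month of each treatment", and a single month has no sample variance. It also avoids the covariance that pairs month j of one condition with month j of another, a pairing with no evident meaning when InForm "allocates each participant a random predefined order during which to take the study interventions".

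State that the target is the population mean, and reconcile this with Protocol 8.1. If the pooled ratio of Protocol 8 is adopted instead, say so and bootstrap whole participants, taking the interval directly with no further division by sqrt(N). In the assumed settings at N = 60, that interval covered 94–95%, with half-width 0.032 where the mean of ratios gave 0.132 (differences of mean 5, SD 3). For the mean of ratios, a percentile bootstrap covered only 88–92% where some differences were near zero, so the t interval is the better default there.

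State also that the correction does not by itself secure ±10%. At N = 60 and share 0.70 the new half-width was 0.060 at 3 monthly SDs, 0.113 at 2 and 0.78 at 1.

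Cost: SAP wording, simpler code and a decision on the estimand. No new data.

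### The variance behind the primary interval and test in SAP 6.1 contains only within-participant noise, so the between-participant scatter on which the ±10% target of SAP 4.1 rests never enters; correcting the scaling alone does not cure this

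*SAP*

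**What the plan says.** SAP 6.1 estimates the mean nocebo effect as the average of N individual ratios, (placebo − no medication)/(statin − no medication). For its precision, it says that "the variance of the estimated mean can be calculated as the sum of variances of the individual participants", that is s² = Σ s_n². Each s_n² is a Taylor approximation, "which is a function of the variance of the numerator, variance of the denominator, and the covariance of the two". The one covariance written out in full sums over a participant's four months, around that participant's own means, with divisor 4−1. The interval is then the mean ± t(α/2, N−1)·√s²/√N, and the test statistic has the same form. If the components are not stable, a bootstrapped variance replaces the Taylor one; the unit to be resampled is not stated.

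SAP 4.1 works at a different level. "The study aims to report an average effect of nocebo for" the population, to within ±10%, "assuming a conservative scenario of individual-participant values scattered uniformly from 0 to 1", which gives an SD of 0.29. It adds: "The investigators planned to recruit 50 participants. In all a total of 62 participants were screened and 60 were randomized".

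Protocol 1.4, section 8, replaces the individual ratios by one ratio pooled over all patients. Section 8.1 says that Hypothesis 2 concerns the participants studied and not a wider population. The SAP (January 2020, based on protocol 1.2) predates protocol 1.4 (April 2020), but its introduction says that the SAP prevails where the two differ on the analyses.

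**The concern.** The trial's precision was planned from one variance and will be reported from another. SAP 4.1 uses only the spread of ratios between people; SAP 6.1 uses only the month-to-month noise within each person. A quick test shows the gap. If every participant had noise-free months and the ratios ran from 0 to 1, SAP 6.1 would give an interval of zero width, although the population mean would still be uncertain by about ±0.08 at N=50. The N−1 degrees of freedom also belong to a between-participant variance that is never computed.

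The primary confidence interval and p-value for the claim that more than half of the symptom burden is nocebo both depend on this. The flaw is easy to miss because scaling errors in the same formula usually push the other way. Someone who corrects only those could turn a very wide interval into one that is too narrow.

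**Working it through.** **1. The plan's own figure.** SAP 4.1 prints (1.96 × 0.29/0.10)² = 36. The expression equals 32.3, so 33. Solving with the t quantile gives 35. The discrepancy is on the safe side and does not affect this point. With SD 0.29 alone, the half-width t·0.29/√N is 0.082 at N=50 and 0.075 at N=60.

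**2. What the printed formula gives.** With s² = Σ s_n², the half-width t·√s²/√N equals t × RMS(s_n). It does not shrink with N, apart from the small change in t. Two scaling faults are present: the variance of a mean of N independent ratios is Σ s_n²/N², not Σ s_n²/√N-type scaling of an undivided sum; and, by the printed covariance, the components are variances of single months, whereas the ratio uses four-month means (a further division by 4).

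**3. Hand calculation for one case.** Assumptions, because the documents give no values: total effect D = 20 points for everyone, independent month error with SD σ = 2, shares r uniform on 0 to 1, N=60, t = 2.001.
- Numerator and denominator variances are each 2σ² and their covariance is σ², so s_n² = (2σ²/D²)(1 − r + r²).
- The average of 1 − r + r² over uniform r is 1 − 1/2 + 1/3 = 5/6, so the mean s_n² = (5/3)(4/400) = 0.0167 and RMS(s_n) = 0.129.
- Printed half-width: 2.001 × 0.129 = 0.26.
- Summing repaired: 0.258/√60 = 0.033. Month variances also divided by 4: 0.017.
- True SE of the mean: √(1/12 + 0.0167/4)/√60 = 0.296/7.746 = 0.038, so a correct half-width is 0.076.
- Coverage: 0.033/0.038 is about 0.87 SE, or 62%; 0.017/0.038 is about 0.44 SE, or 34%.

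**4. Simulation over the assumed noise range** (4,000 trials per scenario, D = 20, N=60, one-sided 5% test at a true share of 50%):

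| Variance used | Quantity | SD 2 | SD 4 | SD 6 |
|---|---|---|---|---|
| Summing repaired only | half-width | 0.034 | 0.070 | 0.113 |
| | coverage | 62% | 90% | 98% |
| | one-sided error | 23% | 8% | 2% |
| Summing and month division repaired | half-width | 0.017 | 0.035 | 0.057 |
| | coverage | 34% | 60% | 77% |
| | one-sided error | 35% | 24% | 16% |

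The formula as printed has half-width 0.26 to 0.88 and coverage 100% across these scenarios at N=50 and 60. The sample SD of the N ratios divided by √N has half-width about 0.08 to 0.10, covers 95% and has one-sided error of about 5%.

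**5. Sensitivity.** With a total effect of 10 points, the interval with both repairs covers about 90% at month SD 4 and 99% at month SD 6.

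**6. A check that does not use D and σ.** Let w be the SD of one person's ratio around its true value. At N=50, the correctly scaled within-person interval covers the population mean 27%, 49%, 75% and 84% of the time for w = 0.05, 0.1, 0.2 and 0.29. It covers the mean of the enrolled sample about 96% of the time.

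**The case against.** A reader might infer that the interval in the SAP is too narrow, or that the primary test as written would produce false positives. The documents do not support that. In every scenario of step 4 the printed formula overcovers and its one-sided error is 0%. It falls below the correct width only if the typical s_n is under about 0.041 at N=50 (50w² = 0.29² + w²); at w = 0.02 it covers 67%. Nor does repairing the summing always lead to serious undercoverage: at month SD 4 coverage is 90%, and at SD 6 it exceeds 95%. The severe figures need both repairs.

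Three further objections carry weight.
- **Target.** Under Protocol 8.1, Hypothesis 2 is about the sample. For that target a within-participant variance is appropriate, as step 6 shows. But the SAP says that it governs, names the population in 4.1, and plans a t test with a p-value. The two documents have not been reconciled, so this is partly an unsettled choice of target.
- **Bootstrap.** A fallback that resamples participants would bring in the missing component. One that resamples months within a person would not. The SAP does not say which, and the fallback applies only if the components are unstable.
- **Estimator.** Protocol 8 leaves individual ratios because they become extreme when statin and no-treatment scores are close. A better variance for their mean does not cure that, which is a separate issue.

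It is also fair to say that this overlaps with the summing error: both lie in the definition of s², and one substitution removes both.

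**Conclusion.** The concern holds as a mismatch between SAP 4.1 and SAP 6.1. For a population target, the variance behind the primary interval and test comes from the wrong source, and this follows from the algebra without any assumed value. It should be corrected before the primary analysis.

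The practical effect depends on what else is changed. Left as printed, the interval is usually several times too wide (0.26 to 0.88 against about 0.08 to 0.10), so the test would have little chance of supporting the hypothesis. With only the scaling corrected, coverage at N=60 ranges from about 34% to 98%, depending on which repairs are made and on the noise. None of these versions is calibrated to 95%, because none contains the scatter between participants. All these sizes rest on assumed uniform shares, a common total effect of 20 points and month SD of 2 to 6; at 10 points the undercoverage after both repairs is milder or absent.

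**What to change.** - In SAP 6.1, define s² as the sample variance of the N individual ratios, with divisor N−1. Keep √s²/√N and t on N−1 df. This contains both sources of variation and also removes the summing and month-division faults.
- State that the bootstrap fallback, and any interval for the pooled ratio of Protocol 8, resamples whole participants.
- Keep the Taylor variance only to describe the precision of one participant's own ratio.
- State one inference target in both documents. SAP 4.1 says the population; Protocol 8.1 says the sample only.

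The cost is a change of SAP wording and simpler code, with no new data. The interval may be wider than one that uses within-participant noise alone. Instability of individual ratios with a small denominator still has to be dealt with separately.
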